7.3.2.5. Overall Survival

Overall survival will be listed for the FAS and is defined as the number of days from randomization in Phase 2 (or first dose of study drug in Phase 1) to death due to any cause. Date of death will be determined using the Death Report, the Survival Follow-Up, and the Participant Status eCRFs. Participants who are lost to follow-up or still alive at the time of analysis will be right-censored at the earlier of the date the participant was last known alive and the clinical data cutoff date for the analysis. The last known alive date is defined as the later of the last study visit and the date the participant was last known alive from the Survival Follow-Up and Participant Status eCRFs.

8. SAFETY AND TOLERABILITY

[Appendix A](#) provides a list of data displays. Sample data displays are included in a separate document.

8.1. General Consideration

Summary tables may be replaced with listings when appropriate. For instance, an AE frequency table may be replaced with a listing if it only contains a few unique PTs reported on relatively few participants.

Unless otherwise stated, table summaries will be limited to TEAEs.

8.2. Adverse Events

8.2.1. Adverse Event Definitions

A TEAE is any AE either reported for the first time or worsening of a pre-existing event after the first dose of study drug. Analysis of AEs (as discussed below) will be limited to TEAEs, but data listings will include all AEs regardless of their timing in relation to study drug administration. For purposes of analysis, all AEs will be considered TEAEs unless the AE can unequivocally be defined as not treatment-emergent.

Adverse events will be tabulated by MedDRA PT and SOC. Severity of AEs will be graded using the NCI CTCAE v5. The CTCAE reporting guidelines and grading details are available on the Cancer Therapy Evaluation Program website.

The subset of AEs considered by the investigator to be related to study drug will be considered to be treatment-related AEs. If the investigator does not specify the relationship of the AE to study drug, the AE will be considered to be treatment-related. The incidence of AEs and treatment-related AEs will be tabulated. In addition, serious TEAEs will also be tabulated.

A grading (severity) scale is provided for each AE term. If the toxicity is not included in the CTCAE v5 criteria, it will be rated on a scale of 1 to 5 as follows: 1 = mild, 2 = moderate, 3 = severe, 4 = life threatening, and 5 = death related to AE. All toxicities will be graded based on the worst level reached, not the level they may have reached if they had not been treated. When the intensity of an AE changes over time for a reporting period (eg, between visits), each change in intensity will be collected as an AE until the event resolves. Only the worst grade will be reported in AE summaries. Also, Grade 3 or higher AEs will be summarized.

Any missing onset date, causality, or severity must be queried for resolution. Unresolved missing causality and severity will be handled according to the following rules:

- An unresolved missing causality will be considered treatment-related.
- An unresolved missing severity will be identified as an unknown severity.

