SIPPM	Site Investigational Product and Procedures Manual
SmPC	summary of product characteristics
■	■
SoA	schedule of activities
SOP	standard operating procedure
SPD	sum of the products of the maximal perpendicular diameters of measured lesions
SPEP	serum M-protein quantitation by electrophoresis
study drug	INCB001158
study treatment	This term refers to all medications that the participant is required to receive as part of this study.
T1DM	Type 1 diabetes mellitus
TAM	tumor-associated macrophages
TCR	T-cell receptor

Abbreviations and Special Terms	Definition
TEAE	treatment-emergent adverse event, AEs reported for the first time or worsening of a pre-existing event after first dose of study treatment
[REDACTED]	[REDACTED]
TSH	thyroid-stimulating hormone
TTR	time to response
ULN	upper limit of normal
UPEP	urine M-protein quantitation by electrophoresis
[REDACTED]	[REDACTED]
VGPR	very good partial response
WBC	white blood cell

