After the equal randomization period, an RAR design will be used to compare the ORR of Treatment Groups A and B with adjustments to the randomization rate based on the observed ORR. Evaluation of the safety and tolerability of the 3 treatment groups will be performed periodically throughout the study. Details of the randomization method and model for response are provided in the Statistical Methods section. Participants will be analyzed for efficacy based on the treatment group in which they were randomized.

[Table 3](#) and [Table 4](#) present the SoA for study site visit assessments prior and post-crossover respectively. [Table 5](#) and [Table 6](#) present the schedule of laboratory assessments prior and post-crossover respectively. As of Protocol Amendment 3, only the SoA presented in [Table 7](#) will be used. [Table 22](#) presents the safety laboratory analytes to be evaluated. Adherence to the study design requirements, including those specified in the SoA, is essential and required for study conduct.

NOTE: As of Protocol Amendment 3, no further disease status and survival follow-up assessments will be required beyond the last safety follow-up visit.

Table 3: Schedule of Activities for Participants in Phase 1, Phase 2, Treatment Group A, Treatment Group B – Part 1 (Prior to Crossover), and Treatment Group C – Part 1 (Prior to Crossover)

Visit Day (Range)	Screening	Treatment (28-day Cycles)								EOT	Follow-Up			Notes	
		Cycles 1 and 2				Cycles 3 to 6		Cycles 7+	Safety	Disease Status	Survival				
		Days -28 to -1	D1	D8 (± 2d)	D15 (± 2d)	D22 (± 2d)	D1 (± 3d)	D15 (± 3d)	D1 (± 3d)	+ 7d	28-35d After EOT	Q8W After EOT ± 7d	Q12W After EOT ± 7d		
Administrative procedures															
Informed consent	X													See Section 8.1.1 .	
Contact IRT	X	X	X	X	X	X	X	X	X					See Section 8.1.3 .	
Inclusion/exclusion criteria	X	X												See Section 5 .	
General and medical history	X													See Section 8.1.5 .	
Prior/concomitant medications	X	X	X	X	X	X	X	X	X					See Section 6.8 .	
Distribute reminder cards		X	X	X	X	X	X	X						See Section 8.1.4 .	
Assess study treatment compliance		X*				X		X	X					* C2D1 only. See Section 6.4 .	
Study treatment															
Dispense/administer INCB001158 (participants receiving INCB001158 monotherapy or in combination with daratumumab SC)		X	X	X	X	X	X	X						In clinic, should be given just before administration of daratumumab SC (if applicable). See Section 6.1 , Appendix B , and refer to the Pharmacy Manual.	

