10.4.2. Safety Analyses

10.4.2.1. Adverse Events

A TEAE is any AE either reported for the first time or worsening of a pre-existing event after first dose of study drug. Analysis of AEs will be limited to TEAEs, but data listings will include all AEs regardless of their timing to study drug administration. Adverse events will be tabulated by the MedDRA preferred term and system organ class for all events and AESIs, including irAEs and potential inhibition of the urea cycle (based on urinary orotic acid, plasma ammonia and urea/BUN assessments). Severity of AEs will be based on the NCI CTCAE v5 using Grades 1 through 5.

The subset of AEs considered by the investigator to have a relationship to study drug will be considered to be treatment-related AEs. If the investigator does not specify the relationship of the AE to study drug, then the AE will be considered treatment-related. The incidence of AEs and treatment-related AEs will be tabulated.

Periodic safety stopping rules will be applied in the Phase 2 portion of the study. See Section [10.5.2.2](#) for details regarding these interim safety analyses.

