4. DATA HANDLING DEFINITIONS AND CONVENTIONS

The term "study drug" refers to INCB001158 only, and "study treatment" refers to INCB001158, daratumumab SC, or the combination of INCB001158 and daratumumab SC.

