4.1. Scheduled Study Evaluations and Study Periods

4.1.1. Day 1

Day 1 is the date that the first dose of study treatment (INCB001158 or daratumumab SC) is administered to the participants.

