4.1.3. Baseline Value

Baseline is the last nonmissing measurement obtained before the first administration of study treatment (INCB001158 or daratumumab SC), unless otherwise defined.

When scheduled assessments and unscheduled assessments occur on the same day and the time of the assessment or time of first dose is not available, use the following convention to determine baseline:

- If both a scheduled and an unscheduled visit are available on the day of the first dose and the time is missing, use the scheduled assessment as baseline.
- If all scheduled assessments are missing on the day of the first dose and an unscheduled assessment is available, use the unscheduled assessment as baseline.

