5.2.2. Phase 2: Expansion

Participants will be randomized 1:1:1 to Treatment Groups A, B, or C as follows:

- Treatment Group A: INCB001158 + daratumumab SC
- Treatment Group B: daratumumab SC monotherapy (Part 1), then crossover to INCB001158 + daratumumab SC (Part 2)
- Treatment Group C: INCB001158 monotherapy (Part 1), then crossover to INCB001158 + daratumumab SC (Part 2)

Treatments will be administrated in 28-day cycles for Treatment Groups A, B, and C.

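### TEAEs are counted from the first INCB001158 dose, so Group B's dated daratumumab-monotherapy AEs drop out of the AE tables while its post-crossover AEs stay in

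*SAP*

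**What the plan says.** The two analysis sections agree with each other. SAP 8.2.1: "A TEAE is any AE either reported for the first time or worsening of a pre-existing event after the first dose of study drug". Protocol 10.4.2.1: "A TEAE is any AE either reported for the first time or worsening of a pre-existing event after first dose of study drug". Both documents reserve *study drug* for the arginase inhibitor; in SAP 4 the term "refers to INCB001158 only", and Protocol 6.1 says the same. *Study treatment* is the wider term, covering either agent or both.

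Elsewhere the anchor is different:

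- The TEAE entry in the Protocol's abbreviation list reads "AEs reported for the first time or worsening of a pre-existing event after first dose of study treatment".
- SAP 4.1.1: "Day 1 is the date that the first dose of study treatment (INCB001158 or daratumumab SC) is administered to the participants".
- SAP 4.1.3: "Baseline is the last nonmissing measurement obtained before the first administration of study treatment (INCB001158 or daratumumab SC), unless otherwise defined".
- The FAS (SAP 5.3.2) admits anyone who received a dose of either agent.

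SAP 8.1 restricts tables to TEAEs by default. SAP 5.2 and 5.3.2 summarise Phase 2 by the group initially assigned, and no split between Part 1 and Part 2 is stated. SAP 8.2.1 also has a default: an AE counts as a TEAE unless it clearly is not one.

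**The concern.** Group B is the daratumumab SC monotherapy arm. Its participants receive no INCB001158 until crossover, and those who never cross over receive none at all. A treatment-emergence clock that starts with INCB001158 therefore does not run during the period Group B is there to describe.

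A secondary objective (SAP Table 1) compares the safety of the combination with daratumumab SC monotherapy. Recruitment ended early and the SAP drops the efficacy analyses, so the safety tables are what remains. If the rule is programmed as written, the control column leaves out dated monotherapy AEs and keeps AEs from the combination it is compared with. Both errors run against a valid comparison.

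**Working it through.** The plan gives no figure to reproduce. The check applies the written rule, then counts which outputs it reaches.

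**1. Classification of AEs with a known onset.** The days are illustrative, and crossover is placed at day 120.

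| AE | First INCB001158 dose | TEAE, *study drug* anchor | TEAE, *study treatment* anchor |
|---|---|---|---|
| Group A, day 20 | day 1 | yes | yes |
| Group C Part 1, day 20 | day 1 | yes | yes |
| Group B Part 1, day 20, crosses over | day 120 | **no** | yes |
| Group B Part 2, day 140 | day 120 | yes | yes |
| Group B, day 20, never crosses over | none | **no** | yes |

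Only Group B monotherapy AEs change. In Phase 1 and Group A, INCB001158 is taken just before daratumumab SC at the clinic visit (Protocol Table 3), and Group C starts on INCB001158. In those groups the two anchors fall together. A Part 1 AE that worsens after the first INCB001158 dose would count under either anchor.

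**2. Overall summary, SAP 8.2.4.** It has 17 rows: 16 TEAE rows and one irAE row.

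- Rows on INCB001158 alone: related, Grade 3 or higher related, serious related, interruption, reduction, discontinuation = 6.
- Rows that can change: 16 − 6 = 10. These are any, serious, Grade 3 or higher and fatal (4); daratumumab-related any, Grade 3 or higher and serious (3); and either-agent-related any, Grade 3 or higher and serious (3).
- The irAE row changes only so far as SAP 8.1 limits it to TEAEs.

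**3. By-term summaries, SAP 8.2.4.** Of 10, five concern INCB001158 alone (related, Grade 3 or higher related, reduction, interruption, discontinuation). 10 − 5 = 5 can change: SOC/PT, PT, Grade 3 or higher, serious, fatal.

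**4. Appendix A.** Of the 10 AE tables (3.2.1 to 3.2.10), five concern INCB001158 alone (3.2.5, 3.2.6, 3.2.8, 3.2.9, 3.2.10). 10 − 5 = 5 can change: 3.2.1 to 3.2.4 and 3.2.7. Table 3.2.1 is the overall summary from step 2, so the others are four further tables. The serious TEAE summary has no table number there.

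**5. Scale, for illustration only.** Protocol 10.5.2.2 puts the historical Grade 4 or higher AE rate on daratumumab monotherapy at 30/156 = 19.2%. The number actually enrolled in Group B is not given, so *n* is an assumption; 10 is the planned size of the equal-randomisation stage. The expected number with such an AE is *n* × 30/156, and the chance of at least one is 1 − (126/156)^*n*.

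| Group B *n* (assumed) | Expected | Chance of at least one |
|---|---|---|
| 3 | 0.6 | 47% |
| 5 | 1.0 | 66% |
| 10 | 1.9 | 88% |

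Under the written rule, any of these with a known onset during monotherapy would be missing from the tables.

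**The case against.** The strongest reply is that this is a slip with one sensible reading. SAP 4.2.1 refers to the first administration of either agent and, in the same bullet, calls it study drug administration. Protocol 10.4.1.2 starts PFS at the first dose of *study drug*; taken literally, a Group B participant's PFS would start at or after progression, which cannot be meant. The abbreviation list uses the wider term, and SAP 8.2.4 plans rows for daratumumab-related TEAEs. All of this makes *study treatment* the probable intent. It also shows that the documents conflict, and the operative section carries the narrower defined term.

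A second reply relies on the default in SAP 8.2.1. That could keep AEs whose onset date stays unresolved. It does not rescue a dated AE that precedes any INCB001158 dose, because under the written definition such an AE is clearly not treatment-emergent. For a participant who never crosses over, no qualifying first dose exists.

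The third reply concerns practical effect, and much of it stands. Phase 2 stopped with few participants. Sparse tables may be replaced by listings (SAP 8.1; 10 or fewer participants in 8.2.4), and listings keep all AEs. From Protocol Amendment 3 only SAEs, AESIs and pregnancies are collected, which limits the non-serious post-crossover AEs that could enter the Group B column. The SAP specifies no safety test. These points bound the harm, but replacement by listings is optional and does not correct the definition.

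Finally, the crossover split is a separate matter, since analysis by initial assignment is a stated choice. The five affected Appendix A tables belong to a standard set that is not in the documents, so whether it already separates the periods cannot be checked or assumed.

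**Conclusion.** The concern holds. As written, the TEAE rule excludes dated monotherapy AEs from the Group B column of the AE tables and retains AEs that start or worsen after crossover, over an unchanged FAS denominator. It reaches 10 of 16 TEAE rows, 5 of 10 by-term summaries and 5 of 10 Appendix A AE tables. Those are counts of outputs that can change; they do not measure bias in incidence, which would need Group B enrolment and the crossover fraction.

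The conclusion assumes that *study drug* carries its defined meaning and that onset dates are known. It does not touch the Phase 1 primary safety objective, the classification of AEs in Group A or Group C, the laboratory, vital-sign and ECG baselines, or the listings. Correcting the anchor alone would still leave Group B mixing monotherapy and combination AEs, as Group C already does. The definition should be corrected before the AE tables are produced.

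**What to change.** - In SAP 8.2.1, define a TEAE from the first dose of study treatment (INCB001158 or daratumumab SC), matching SAP 4.1.1 and the Protocol's abbreviation list. Correct Protocol 10.4.2.1 if the Protocol is amended for another reason; an amendment for this alone is not required.
- State that Group B and Group C AEs are summarised separately before and after the first dose of the crossover combination.
- Optionally, align the general relatedness sentence in 8.2.1, which also refers only to *study drug*, with the agent-specific and either-agent rows in 8.2.4. The conclusion does not depend on this.

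The cost is one changed term, one or two sentences, and a split in the AE tables for two groups. AE start dates (Protocol 9.3) and dosing of both agents (SAP 6.4.1 and 6.4.2) are already recorded, so nothing new has to be collected.

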8.2.2. Dose-Limiting Toxicities

Participants in the DLT evaluable population with DLTs and the type of DLT will be listed by dose level and treatment group. An AE for a participant will be identified as a DLT if the event is recorded as a Protocol-defined DLT on the Adverse Event eCRF.

8.2.3. Adverse Events of Special Interest

Adverse events of special interest include irAEs that are seen with immunotherapy and potential inhibition of the urea cycle (based on urinary orotic acid, plasma ammonia, and BUN/urea assessments).

An overall summary of irAEs will include number (%) of participants reporting any irAEs.

8.2.4. Adverse Event Summaries

An overall summary of AEs by dose level for Phase 1 and by treatment group for Phase 2 using the FAS population as applicable will include the following:

- Number (%) of participants reporting any TEAEs
- Number (%) of participants reporting any serious TEAEs
- Number (%) of participants reporting any Grade 3 or higher TEAEs
- Number (%) of participants who had a fatal TEAE
- Number (%) of participants who had a TEAE related to INCB001158
- Number (%) of participants who had a TEAE related to daratumumab SC
- Number (%) of participants who had a TEAE related to INCB001158 and/or daratumumab SC
- Number (%) of participants who had a Grade 3 or higher TEAE related to INCB001158
- Number (%) of participants who had a Grade 3 or higher TEAE related to daratumumab SC
- Number (%) of participants who had a Grade 3 or higher TEAE related to INCB001158 and/or daratumumab SC
- Number (%) of participants who had a serious TEAE related to INCB001158
- Number (%) of participants who had a serious TEAE related to daratumumab SC
- Number (%) of participants who had a serious TEAE related to INCB001158 and/or daratumumab SC

- Number (%) of participants who had a TEAE leading to temporary interruption of INCB001158
- Number (%) of participants who had a TEAE leading to INCB001158 dose reduction
- Number (%) of participants who had a TEAE leading to permanent discontinuation of INCB001158
- Number (%) of participants who had an irAE

The following summaries will be produced by MedDRA term for the Phase 1 and Phase 2 FAS population (if 10 or fewer participants appear in a table, a listing may be appropriate):

- Summary of TEAEs by SOC and PT
- Summary of TEAEs by PT in decreasing order of frequency
- Summary of Grade 3 or higher TEAEs by PT in decreasing order of frequency
- Summary of serious TEAEs by PT in decreasing order of frequency
- Summary of INCB001158 treatment-related TEAEs by PT in decreasing order of frequency
- Summary of Grade 3 or higher INCB001158 treatment-related TEAEs by PT in decreasing order of frequency
- Summary of TEAEs with a fatal outcome by SOC and PT
- Summary of TEAEs leading to INCB001158 dose reduction by PT in decreasing order of frequency
- Summary of TEAEs leading to INCB001158 dose interruption by PT in decreasing order of frequency
- Summary of TEAEs leading to discontinuation of INCB001158 by PT in decreasing order of frequency

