6.7.4. Dose Delays and Dose Modification of Daratumumab SC

Dose modification of daratumumab SC is not permitted. Dose delay is the primary method for managing toxicities related to daratumumab SC.

On the first day of each new treatment cycle and before each daratumumab SC administration, the participant will be evaluated by the treating physician for possible toxicities that may have occurred after the previous dose(s). Toxicities are to be assessed according to CTCAE v5. Dose delays will be made based on the toxicity experienced during the previous cycle of therapy or newly encountered on Day 1 of a cycle.

For all daratumumab SC doses in a treatment cycle except the first dose, if daratumumab SC administration does not commence within the prespecified window (see [Table 3](#) and [Table 4](#) for study site visit assessments prior to and post-crossover, respectively, and [Table 7](#) for all participants as of Protocol Amendment 3) of the scheduled administration date, then the dose will be considered a missed dose. Administration may resume at the next planned dosing date. A missed dose will not be made up. The minimal time interval between daratumumab SC doses should be 4 days.

Daratumumab SC treatment must be held if any of the following criteria below are met, to allow for recovery from toxicity, regardless of relationship to INCB001158 or daratumumab SC.

- Grade 4 hematologic toxicity, except for Grade 4 lymphopenia
- Grade 3 thrombocytopenia with bleeding
- Febrile neutropenia
- Neutropenia with infection, of any grade
- Grade 3 or higher nonhematologic toxicities, *with the following exceptions:*
 - Grade 3 nausea or Grade 3 vomiting that responds to antiemetic treatment within 7 days
 - Grade 3 diarrhea that responds to antidiarrheal treatment within 7 days

- Grade 3 fatigue that was present at baseline or that lasts for < 7 days after the last administration of daratumumab SC
- Grade 3 asthenia that was present at baseline or that lasts for < 7 days after the last administration of daratumumab SC.

Administration of daratumumab SC may be restarted (as indicated in [Table 18](#)) upon recovery from toxicity to Grade 2 or baseline, with the exception that Grade 2 laryngeal edema or Grade 2 bronchospasm must be fully recovered.

Table 18: Daratumumab SC-Related Toxicity Management

Cycles	Frequency	Dose Held	Dosing Re-Start at
1 and 2	QW	> 3 days	Next planned QW dosing date
3 to 6	Q2W	> 7 days	Next planned Q2W dosing date

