9.3. Recording and Follow-Up of Adverse Events and/or Serious Adverse Events

Adverse Event and Serious Adverse Event Recording

- An AE/SAE that begins or worsens after informed consent is signed should be recorded on the Adverse Event Form in the eCRF. Conditions that were present at the time informed consent was given should be recorded on the Medical History Form in the eCRF.
- When an AE/SAE occurs, it is the responsibility of the investigator to review all documentation (eg, hospital progress notes, laboratory reports, and diagnostics reports) related to the event.
- The investigator (or delegate) will then record all relevant AE/SAE information in the eCRF.
- It is **not** acceptable for the investigator to send photocopies of the participant's medical records in lieu of completing the AE eCRF page.
- There may be rare instances when copies of medical records for certain cases are requested. In this case, all participant identifiers, with the exception of the participant number, will be redacted on the copies of the medical records before submission. These records can be submitted to Incyte Pharmacovigilance by email/fax per the contact information listed in the Study Reference Manual or as per SAE completing guidelines.
- The investigator will attempt to establish a diagnosis of the event based on signs, symptoms, and/or other clinical information. Whenever possible, the diagnosis (not the individual signs/symptoms) will be documented as the AE/SAE. When a clear diagnosis cannot be identified, each sign or symptom should be reported as a separate AE/SAE.

To the extent possible, each AE/SAE should be evaluated to determine:

- The severity grade (CTCAE v5.0 Grade 1 to 5). See below for further instructions on the assessment of intensity.
- Whether there is at least a reasonable possibility that the AE is related to the study treatment (including INCB001158 and/or daratumumab SC): suspected (yes) or not suspected (no). See below for further instructions on the assessment of causality.
- The start and end dates, unless unresolved at final safety follow-up visit.
- The action taken with regard to INCB001158 and/or daratumumab SC as a result of the AE/SAE(s).
- The event outcome (eg, not recovered/not resolved, recovered/resolved, recovering/resolving, recovered/resolved with sequelae, fatal, unknown).
- The seriousness, as per the SAE definition provided in Section 9.2.

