2.2. Study Objectives and Endpoints

[Table 1](#) presents the objectives and endpoints.

Due to early termination decision following recruitment challenge (no safety-related concerns), primary safety analyses but no efficacy analyses will be performed due to insufficient number of participant enrolled in Phase 2.

Table 1: Objectives and Endpoints

Objectives	Endpoints
Primary	
Phase 1: To determine the safety, tolerability, and RP2D of INCB001158 in combination with daratumumab SC.	Safety and tolerability determined by monitoring the frequency, duration, and severity of AEs.
Phase 2: To compare the ORR of the RP2D of INCB001158 in combination with daratumumab SC to daratumumab SC monotherapy.	ORR, defined as the proportion of participants with a documented response PR or better, as per IMWG criteria.
Secondary	
Phase 1: To determine the efficacy of INCB001158 in combination with daratumumab SC.	ORR, defined as the proportion of participants with a documented response PR or better, as per IMWG criteria.
Phase 2: To determine the safety and tolerability of INCB001158 monotherapy at RP2D, and to compare the safety and tolerability and RP2D of INCB001158 in combination with daratumumab SC to daratumumab SC monotherapy	Safety and tolerability determined by monitoring the frequency, duration, and severity of AEs.
Phase 1: To determine the efficacy of INCB001158 in combination with daratumumab SC. Phase 2: To estimate the efficacy of INCB001158 monotherapy, and to compare the efficacy of INCB001158 in combination with daratumumab SC to daratumumab SC monotherapy.	
• TTR, defined as the time from the first dose of study drug to the first documented response PR or better, as per IMWG criteria.• DOR, defined as time from first documented response PR or better, as per IMWG criteria, until date of disease progression or death, whichever occurs first.• PFS, defined as the duration from the date of first dose of study drug until either PD, as per IMWG criteria, or death, whichever occurs first.• MRD, defined as the percentage of MRD-negative participants.• OS, defined as the time from the first dose of study drug to death from any cause.

Table 1: Objectives and Endpoints (Continued)

Objectives	Endpoints

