3.2.8	Summary of Treatment-Emergent Adverse Events Leading to INCB001158 Dose Reduction by MedDRA Preferred Term in Decreasing Order of Frequency	FAS	
3.2.9	Summary of Treatment-Emergent Adverse Events Leading to INCB001158 Dose Interruption by MedDRA Preferred Term in Decreasing Order of Frequency	FAS	
3.2.10	Summary of Treatment-Emergent Adverse Events Leading to Discontinuation of INCB001158 by MedDRA Preferred Term in Decreasing Order of Frequency	FAS	
3.3.1.1	Summary of Laboratory Values - Hematology	FAS	X
3.3.1.2	Summary of Laboratory Values - Chemistry	FAS	X
3.3.3.4	Treatment-Emergent Worsening of Laboratory Abnormalities - Hematology	FAS	X
3.3.3.5	Treatment-Emergent Worsening of Laboratory Abnormalities - Chemistry	FAS	X
3.4.1	Summary of Systolic Blood Pressure	FAS	X
3.4.2	Summary of Diastolic Blood Pressure	FAS	X
3.4.3	Summary of Pulse	FAS	X
3.4.4	Summary of Respiratory Rate	FAS	X
3.4.5	Summary of Body Temperature	FAS	X
3.4.6	Summary of Body Weight	FAS	X
3.5.1	Summary of PR Interval (ms) From 12-Lead ECG	FAS	X
3.5.2	Summary of QRS Interval (ms) From 12-Lead ECG	FAS	X
3.5.3	Summary of QT Interval (ms) From 12-Lead ECG	FAS	X
3.5.4	Summary of QTcF Interval (ms) From 12-Lead ECG	FAS	X
3.5.5	Summary of RR Interval (ms) From 12-Lead ECG	FAS	X
3.5.6	Summary of Heart Rate (bpm) From 12-Lead ECG	FAS	X
3.5.7	Summary of Outliers of QT and QTcF Interval Values (ms) From 12-Lead ECG	FAS	X

Listings

Listing No.	Title
2.1.2.x	Participant Enrollment and Disposition Status
2.2.1.x	Participant Inclusion and Exclusion Criteria Violations
2.2.2.x	Protocol Deviations
2.3.1.x	Analysis Populations
2.4.1.x	Demographics and Baseline Characteristics
2.4.2.x	Baseline Disease Characteristics
2.4.3.x	Prior Radiation Treatment
2.4.4.x	Prior Therapy for Disease Under Study
2.4.5.x	Prior Surgery or Surgical Procedure
2.4.6.x	Medical History
2.4.7.x	Prior and Concomitant Medications
2.4.8.x	Post-Treatment Anticancer Therapy
2.5.1.x	Study Drug Administration for INCB001158
2.5.2.x	Study Drug Compliance for INCB001158
2.5.3.x	Study Drug Administration for Daratumumab SC
2.6.1.x	Overall Response Assessments and Best Overall Response Under IMWG Criteria
2.6.2.x	Efficacy Endpoints (TTR, DoR, PFS, and OS)
2.6.3.x	ECOG Status
2.6.4.x	Clinical Laboratory Values – Chemistry, SPEP
2.6.5.x	Clinical Laboratory Values – Immunology
2.6.6.x	Clinical Laboratory Values – Immunology, Free Light Chains
2.6.7.x	Clinical Laboratory Values – Immunology, Immunofixation

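### SAP displays of AEs that led to a treatment change cover INCB001158 only; AEs leading to a hold or stop of daratumumab SC, or to a stop of any study treatment, have no display of their own

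*SAP*

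**What the plan says.** The overall AE summary in SAP 8.2.4 has three rows on the consequence of an event for treatment: "Number (%) of participants who had a TEAE leading to temporary interruption of INCB001158", "Number (%) of participants who had a TEAE leading to INCB001158 dose reduction" and "Number (%) of participants who had a TEAE leading to permanent discontinuation of INCB001158". The same section plans three matching summaries by preferred term. Appendix A carries these as Tables 3.2.8 to 3.2.10, the last titled "Summary of Treatment-Emergent Adverse Events Leading to Discontinuation of INCB001158 by MedDRA Preferred Term in Decreasing Order of Frequency". The one dedicated listing, 2.7.5, is also confined to INCB001158.

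For causality the same overall summary treats the two agents alike. It includes "Number (%) of participants who had a TEAE related to daratumumab SC", repeats that row for Grade 3 or higher and for serious events, and adds three rows for either agent.

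The protocol expects AEs to change daratumumab treatment. Section 6.7.4 states: "Dose delay is the primary method for managing toxicities related to daratumumab SC". It lists toxicities for which daratumumab must be held, and Table 15 requires permanent discontinuation after certain injection-related reactions. Protocol 9.3 asks the site to evaluate, for each event, "The action taken with regard to INCB001158 and/or daratumumab SC as a result of the AE/SAE(s".

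Among the Phase 2 secondary objectives in SAP Table 1 is "to compare the safety and tolerability and RP2D of INCB001158 in combination with daratumumab SC to daratumumab SC monotherapy".

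**The concern.** After early termination the SAP keeps safety analyses only (SAP 3 and 10.1). The Phase 1 primary objective is the tolerability of the two-drug regimen, and a Phase 2 secondary objective sets that regimen against daratumumab alone. For both, a basic measure is how many participants had treatment interrupted or stopped because of an AE.

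The planned displays answer that for one of the two agents. In Phase 1 and Group A they leave out AEs that affected only the daratumumab component. In Group B they cannot describe the monotherapy period, because no INCB001158 is given then. Neither the regimen's rate of AE-related discontinuation nor the monotherapy comparator can be read from them.

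**Working it through.** No figure in the plan is at issue, so the check is a count of displays followed by a trace of participants through them.

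**Step 1. Count the action-taken displays by agent (SAP 8.2.4 and Appendix A).**

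| Type of display | Planned | INCB001158 | Daratumumab SC | Any study treatment |
|---|---|---|---|---|
| Overall summary rows | 3 | 3 | 0 | 0 |
| Preferred-term summaries (Tables 3.2.8 to 3.2.10) | 3 | 3 | 0 | 0 |
| Same three as listed in Appendix A | 3 | 3 | 0 | 0 |
| Dedicated listing (2.7.5) | 1 | 1 | 0 | 0 |

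The sum is 3 + 3 + 3 + 1 = 10 entries, all for INCB001158. Rows two and three are the same outputs named in two places, so there are 3 + 3 + 1 = 7 distinct displays, again all for INCB001158. Tables 3.2.1 to 3.2.10 and Listings 2.7.1 to 2.7.6 are numbered without a gap, so redaction is an unlikely explanation.

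**Step 2. Can one agent be held or stopped without the other?** Yes for holds: protocol 6.7.4 lets INCB001158 continue, with medical monitor approval, while daratumumab is held. For permanent stops, Table 15 takes the participant off daratumumab, not off all study treatment, and protocol 7.1.1 does not list this as a reason to stop everything. That INCB001158 may then continue is my reading; the text does not state it outright.

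**Step 3. Trace each case.**

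| Case | Action-taken displays | Disposition (SAP 6.2, Table 1.1.3) |
|---|---|---|
| Phase 1 or Group A, daratumumab held for an AE | Not counted | Not counted |
| Phase 1 or Group A, daratumumab stopped for an AE, INCB001158 continues | Not counted | Not counted at that point; the end-of-treatment visit needs all study treatment stopped (protocol 8.7) |
| Group B Part 1, daratumumab held for an AE | Not counted | Not counted |
| Group B Part 1, daratumumab stopped for an AE | Not counted | Counted by primary reason, without the AE term |
| Group B Part 2, INCB001158 held, reduced or stopped for an AE | Counted under Group B | Only if all treatment stops |

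The last row follows from SAP 5.3.2, which analyses participants by initial assignment, and SAP 5.2, which summarises Phase 2 by treatment group. Neither separates Part 1 from Part 2.

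**Step 4. Look for a substitute.** Daratumumab exposure (SAP 6.4.2) gives number of administrations, average dose and dose per cycle, with no link to an AE. The general AE listing (2.7.1) may carry an action-taken column, but the shells are in a separate document. Even so, a general listing is not a count.

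**The case against.** Two stronger readings are tempting, and the documents support neither.

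- *A reader might infer that treatment-stopping toxicity of daratumumab is tabulated nowhere.* That goes too far. In Group B Part 1 daratumumab is the whole study treatment and crossover occurs only at confirmed progression. A participant who stops it for toxicity has stopped all treatment and enters the disposition table under a primary reason. The reason categories are not shown, and the AE term is absent, but the stop is counted.
- *A reader might infer that the Group B column is zero by construction.* That holds for Part 1 only. The planned column is unsplit and as assigned, so events after crossover can make it non-zero. For dose reduction, a Part 1 zero is simply correct, because protocol 6.7.4 does not permit daratumumab dose modification.

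There are further fair points. Every row is labelled INCB001158, so a careful reader would not take it for a regimen rate. Phase 2 enrolled few participants, the safety summaries are descriptive, and no analysis of A against B on discontinuation is specified. Daratumumab toxicity also shows in the relatedness rows and in the DLT listing. The protocol's general AE section (10.4.2.1) promises no action-taken tables. Only its irAE summary (10.4.2.5) mentions treatment interruption, reduction or discontinuation, so for TEAEs in general this is a request for more and not a broken commitment.

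These points limit the consequence. They do not supply the missing information: none identifies the AE behind a daratumumab hold or stop, and none counts daratumumab-only stops in combination participants.

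**Conclusion.** The gap is real and moderate. All seven distinct action-taken displays are for INCB001158; none is for daratumumab SC or for any study treatment. AEs that changed only daratumumab treatment are therefore not counted in these displays for Phase 1 or Group A. Group B Part 1 contributes nothing to them, and a Group B count can arise only from INCB001158 taken after crossover. Disposition covers full stops by primary reason but lacks AE terms, holds or delays, and daratumumab-only stops.

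The practical weight is greatest in Phase 1, where combination tolerability is the primary objective and one of two agents is left out. I put no percentage on the number of missed events, since the documents give no rate of daratumumab-only holds or stops.

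The conclusion assumes that the eCRF records action taken separately for each agent, as protocol 9.3 implies; the form itself is not among the documents.

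**What to change.** In the SAP 8.2.4 overall summary, add rows for TEAEs leading to:

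- (a) interruption or delay of daratumumab SC;
- (b) permanent discontinuation of daratumumab SC;
- (c) permanent discontinuation of any study treatment.

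Add matching preferred-term tables after 3.2.10, or listings under the SAP's existing allowance when 10 or fewer participants would appear. Extend Listing 2.7.5 to daratumumab SC. No row for daratumumab dose reduction is needed.

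Present Part 1 separately from Part 2 for Groups B and C, and use Group B Part 1 only when reading Group A against daratumumab monotherapy. Without that split, row (c) would mix monotherapy and combination events in Group B.

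The cost is a few more descriptive rows or listings from action-taken data that protocol 9.3 already calls for. Appendix A describes its lists as guidelines. Two limits should be footnoted. From Amendment 3 on, only SAEs, AESIs and pregnancies are collected, so other nonserious events after that point will be missing. If the eCRF does not code daratumumab delay separately from interruption, row (a) should follow whatever category it does record.
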